Life-threatening or disabling bleeding: Fatal bleeding (*BARC type 5*) **OR**, bleeding in a critical organ, such as intracranial, intraspinal, intraocular, or pericardial necessitating pericardiocentesis, or intramuscular with compartment syndrome (*BARC type 3b and 3c*) **OR**, bleeding causing hypovolemic shock or severe hypotension requiring vasopressors or surgery (*BARC type 3b*) **OR**, overt source of bleeding with drop in hemoglobin ≥ 5 g/dL or whole blood or packed red blood cells (RBCs) transfusion ≥ 4 units¹⁰ (*BARC type 3b*)⁸⁸

Major Bleeding: Overt bleeding either associated with a drop in the hemoglobin level of at least 3.0 g/dL or requiring transfusion of 2 or 3 units of whole blood/RBC, **OR** causing hospitalization or permanent injury, **OR** requiring surgery **AND** does not meet criteria of life-threatening or disabling bleeding.

Minor bleeding: Any bleeding worthy of clinical mention (eg, access site hematoma) that does not qualify as life-threatening, disabling, or major.

Acute Kidney Injury (up to 7 days post procedure)

Stage 1: Increase in serum creatinine to 150%-199% (1.5-1.99 x increase compared with baseline) **OR**, increase of ≥ 0.3 mg/dL (≥ 26.4 mmol/L) **OR**, Urine output < 0.5 mL/kg/h for > 6 but < 12 h

Stage 2: Increase in serum creatinine to 200%-299% (2.0%-2.99% increase compared with baseline) **OR**, Urine output < 0.5 mL/kg/h for ≥ 12 but < 24 h

Stage 3: Increase in serum creatinine to $\geq 300\%$ (> 3 x increase compared with baseline) **OR**, serum creatinine of ≥ 4.0 mg/dL (≥ 354 mmol/L) with an acute increase of at least 0.5 mg/dL (44 mmol/L) **OR**, urine output < 0.3 ml/kg/h for ≥ 24 h **OR**, anuria for ≥ 12 h

¹⁰ Given one unit of packed RBC typically will raise hemoglobin concentration by 1 g/dL, an estimated decrease in hemoglobin will be calculated. A bleeding complication has to be the result of overt bleeding and cannot be adjudicated based on blood transfusions alone.

Vascular Access Site and Access Related Complications

Major vascular complication:

- 1) Any aortic dissection, aortic rupture, annulus rupture, left ventricle perforation, or new apical aneurysm/pseudoaneurysm **OR**,

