- 2) Access site or access-related vascular injury (dissection, stenosis, perforation, rupture, arterio-venous fistula, pseudoaneurysm, hematoma, irreversible nerve injury, compartment syndrome, percutaneous closure device failure) *leading to death, life-threatening or major bleeding, visceral ischemia, or neurological impairment* **OR**,
- 3) Distal embolization (noncerebral) from a vascular source requiring surgery or resulting in amputation or irreversible end-organ damage **OR**,
- 4) Use of unplanned endovascular or surgical intervention associated with death, major bleeding, visceral ischemia or neurological impairment **OR**,
- 5) Any new ipsilateral lower extremity ischemia documented by patient symptoms, physical exam, and/or decreased or absent blood flow on lower extremity angiogram **OR**,
- 6) Surgery for access site-related nerve injury **OR**,
- 7) Permanent access-site related nerve injury

Minor vascular complication

- 1) Access site or access-related vascular injury (dissection, stenosis, perforation, rupture, arterio-venous fistula, pseudoaneurysms, hematomas, percutaneous closure device failure) *not leading to death, life-threatening or major bleeding¹¹, visceral ischemia, or neurological impairment* **OR**,
- 2) Distal embolization treated with embolectomy and/or thrombectomy and not resulting in amputation or irreversible end-organ damage **OR**,
- 3) Any unplanned endovascular stenting or unplanned surgical intervention not meeting the criteria for a major vascular complication **OR**,
- 4) Vascular repair or the need for vascular repair (via surgery, ultrasound-guided compression, transcatheter embolization, or stent-graft)

Percutaneous closure device failure: Failure of a closure device to achieve hemostasis at the arteriotomy site leading to alternative treatment (other than manual compression or adjunctive endovascular ballooning)

Valve Dysfunction Requiring Repeat Procedure: Any valve dysfunction that requires repeat procedure (e.g. balloon valvuloplasty, TAVR, snare repositioning, placement of vascular plug paravalvular leak, or surgical AVR)

¹¹ Refer to bleeding definitions

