7.9 Evaluation of Objectives

7.9.1 Safety Endpoints

The following safety endpoints are defined and will be analyzed:

1. All-cause and cardiovascular mortality at 30 days and 6 months
2. All stroke (disabling and non-disabling) at 30 days and 6 months
3. Myocardial infarction (periprocedural and spontaneous) at 30 days and 6 months
4. Acute kidney injury at 30 days and 6 months
5. Major vascular complications at 30 days and 6 months
6. Life-threatening bleed at 30 days and 6 months
7. New permanent pacemaker implantation (PPI) at 30 days and 6 months
8. New intraventricular conduction delays at 30 days and 6 months
9. New-onset atrial fibrillation at 30 days and 6 months
10. Valve-related dysfunction requiring repeat procedure at 30 days and 6 months

Safety endpoints will be adjudicated by the Clinical Events Committee (CEC) and analysis will be based on data collected on the CEC adjudication form. Safety endpoints will be analyzed with Kaplan-Meier survival analysis methods according to Section 7.2. Safety endpoints will be analyzed using the Attempted Implant population.

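### Major vascular criterion 4 omits life-threatening bleeding, so in a rare case a worse bleed moves an event out of safety endpoint 5; major-over-minor precedence is also unstated

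*Protocol*

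**What the plan says.** Protocol 13.8.1 lists seven major vascular criteria joined by OR, followed by four minor criteria. Protocol 13.8 has the Clinical Events Committee (CEC) code safety endpoints to these definitions. Only the major class is an endpoint: SAP 7.9.1 lists "Major vascular complications at 30 days and 6 months" as safety endpoint 5, analyzed by Kaplan-Meier on CEC-adjudicated events in the Attempted Implant set.

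The texts that matter are these.

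- **Major item 2** covers access-site or access-related injury "leading to death, life-threatening or major bleeding, visceral ischemia, or neurological impairment".
- **Major item 4** covers "Use of unplanned endovascular or surgical intervention associated with death, major bleeding, visceral ischemia or neurological impairment".
- **Major bleeding**, in the same section, is limited to bleeding that "does not meet criteria of life-threatening or disabling bleeding".
- **Minor item 3** takes "Any unplanned endovascular stenting or unplanned surgical intervention not meeting the criteria for a major vascular complication".
- **Major item 3** is "Distal embolization (noncerebral) from a vascular source requiring surgery or resulting in amputation or irreversible end-organ damage".
- **Minor item 2** is "Distal embolization treated with embolectomy and/or thrombectomy and not resulting in amputation or irreversible end-organ damage".
- **Minor item 4** covers vascular repair, or the need for it, with no exclusion for events that are already major.

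**The concern.** There are two separate matters.

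The first is a gap. Item 2 names both upper bleeding classes and item 4 names only one. Because major bleeding is defined to exclude life-threatening bleeding, the omission cannot be read as the larger class containing the smaller. Item 4 is therefore not monotone in severity: worsening the bleed can remove major status. What is at stake is the rate for endpoint 5, in a study with a primary objective of estimating event rates for pivotal trials (Protocol 4.1).

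The second is an overlap. Some events satisfy a major and a minor criterion at once, and neither document says which class prevails. What is at stake there is consistent coding.

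**Working it through.** The plan gives no expected rate of major vascular complications to reproduce. The check is therefore a reading of the rules, followed by the size of one re-coded subject.

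**Bleeding gap.** Take two non-fatal overt bleeds that differ only in transfusion: 3 units (major bleeding) and 4 units (life-threatening). Every row has an unplanned stent or operation and meets none of major items 1, 3, 5, 6 or 7. No row has death, visceral ischemia or neurological impairment.

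| Access-related injury leading to the bleed | Bleed | Major items met | Class as written | Class if item 4 matched item 2 |
|---|---|---|---|---|
| No | 3 units | 4 | Major | Major |
| No | 4 units | none | Minor (item 3) | Major (item 4) |
| Yes | 3 units | 2 and 4 | Major | Major |
| Yes | 4 units | 2 | Major | Major |

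Only the second row is misplaced. A wider check crossed access injury (yes/no), unplanned intervention (yes/no), distal embolus (none, percutaneous removal, surgical removal) and new leg ischemia (yes/no), which is 2 × 2 × 3 × 2 = 24 combinations. Item 1, nerve injury and the other item 4 triggers were held absent, and minor item 4 was left out. Going from a major to a life-threatening bleed removed major status in 2 of the 24. Both had an unplanned intervention, no access-related injury and no leg ischemia; one had no embolus and the other an embolus removed percutaneously.

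**Embolectomy and repair.** Major item 3 has three triggers: surgery, amputation and irreversible end-organ damage. Minor item 2 excludes the last two but not surgery. A surgical embolectomy without tissue loss therefore meets both, while percutaneous removal alone meets only minor item 2. A surgically repaired major injury likewise also meets minor item 4. Because the major list is joined by OR, each of these events does meet the major definition.

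**Size.** Assumptions: 75 subjects in the Attempted Implant set (the plan's figure is a cap on implanted subjects), no censoring, and illustrative event counts. One subject moves the rate by 1/75 = 1.33 points, or 1/50 = 2.0 points at an initial analysis of 50.

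SAP 7.2 specifies a log-log interval with the Greenwood standard error. With S = 1 − x/n and no censoring:

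- SE = √[S(1−S)/n]
- s = SE / (S·|ln S|)
- limits for the event rate: 1 − S^exp(±1.96·s)

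For x = 3: S = 0.96, SE = √(0.96 × 0.04/75) = 0.0226, s = 0.0226/(0.96 × 0.0408) = 0.577. The rate is 4.0% (95% CI 1.3 to 11.9).

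For x = 2: S = 0.9733, SE = 0.0186, s = 0.0186/(0.9733 × 0.0270) = 0.707. The rate is 2.7% (95% CI 0.7 to 10.2).

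**The case against.** The strongest reply is that the downgrade is close to empty. The criteria sit under a heading about access-site and access-related complications, and access must be transfemoral (Protocol 6.19). Item 2 already makes major any listed access-related injury that leads to life-threatening bleeding. Item 1 covers aortic or annular rupture and ventricular perforation whatever the bleed. Item 5 separately covers "Any new ipsilateral lower extremity ischemia documented by patient symptoms, physical exam, and/or decreased or absent blood flow on lower extremity angiogram". Item 4 itself still catches death, visceral ischemia and neurological impairment. This stands, and it limits the point to rare events. It does not make item 4 redundant: item 2 needs an injury that leads to the bleed, whereas item 4 needs only an intervention associated with it.

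The second reply is that the harm is not lost. A life-threatening bleed is itself safety endpoint 6, in the same analysis set and by the same method, and it also appears in the adverse event tables (SAP 7.10). This stands in full.

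A reader might also infer that the embolectomy and repair overlaps cause under-counting. The documents do not support that. Endpoint 5 asks only whether a major criterion was met, and also meeting a minor one subtracts nothing. An event would be lost only if the CEC set aside a satisfied major criterion, and no text tells it to.

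Finally, the definitions are attributed to VARC-2, and the CEC charter and code list are not among the documents. A tie-break may exist there, so the precedence point is only that the protocol and SAP do not state one. The item 4 wording is on the page either way. Footnote 12 in Protocol 13.8.3, on patient-prosthesis mismatch, shows the sponsor already departing openly from a VARC-2 definition in this appendix.

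**Conclusion.** The point holds in a narrow form. Item 4 as written sends an item-4-only event with a non-fatal life-threatening bleed to minor item 3, and so out of endpoint 5, while the same event with a lesser, major bleed stays in. This is a wrong rule rather than a missing detail, but it affects only events not caught by another major item or another item 4 trigger. The overlaps are a precedence ambiguity.

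A broader conclusion, that the vascular definitions contradict each other and that endpoint 5 or overall harm is materially under-counted, is not supported. The effect is 1.3 points per re-coded subject at n=75, and the event counts used above are assumptions. The study is descriptive, so no hypothesis test or decision rule is touched. This is a minor, worthwhile correction.

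**What to change.** 1. In major item 4, use the same four consequences as item 2: death, life-threatening or major bleeding, visceral ischemia, neurological impairment. Mark it as a clarification of the cited VARC-2 text, as footnote 12 does for patient-prosthesis mismatch.
2. Head the minor list with a statement that it applies only when no major criterion is met. Surgical embolectomy is then coded under major item 3, and a repaired major injury stays major.
3. Carry both lines into the CEC charter, and have the CEC re-check vascular events already coded minor.

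The cost is two lines of text and re-reading the vascular events already coded minor. The downside is a small departure from the cited definition, which slightly affects comparability with rates coded to the published wording, and a reported major vascular rate that may rise slightly.

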13.8.2 Other TAVR Related Complications⁶³

Conversion to open surgery: Conversion to open sternotomy during the TAVR procedure secondary to any procedure-related complications.

Unplanned use of cardiopulmonary bypass: Unplanned use of CPB for hemodynamic support at any time during the TAVI procedure.

Coronary artery obstruction: Angiographic or echocardiographic evidence of a new, partial or complete, obstruction of a coronary ostium, either by the TAV prosthesis itself, the native leaflets, calcifications, or dissection, occurring during or after the TAVR procedure.

Ventricular septal perforation: Angiographic or echocardiographic evidence of a new septal perforation during or after the TAVR procedure

Mitral valve apparatus damage or dysfunction: Angiographic or echocardiographic evidence of new damage (chordae, papillary muscle, or leaflet) to the mitral valve apparatus or dysfunction (e.g. restrictions due to the TAV of the mitral valve during or after the TAVR procedure.

Cardiac tamponade: Evidence of new pericardial effusion associated with hemodynamic instability and clearly related to the TAVI procedure.

Prosthetic valve thrombosis:

1. Clinical: Any thrombus not caused by infection attached to or near the trial valve that occludes part of the blood flow path, interferes with valve function, or is sufficiently large to warrant treatment which is associated with any of the following clinical sequelae:

- Thromboembolic complications including
 - Any ischemic stroke
 - Any peripheral embolic event
 - ST segment elevation or Non-ST elevation myocardial infarction
 - Hemodynamic impairment associated with a worsening of heart failure

Note: valve thrombus found at autopsy in a subject whose cause of death was not valve-related or found at operation for an unrelated indication should be reported as valve thrombosis

2. Sub-Clinical: Any thrombus not caused by infection attached to or near the trial valve that occludes part of the blood flow path or interferes with valve function, without evident clinical sequelae, causing a hemodynamic impediment meeting the following criteria:

- Increase in aortic regurgitation to moderate to severe.
- An increase by more than 50% of discharge mean aortic valve gradient (with the post discharge mean gradient being ≥ 20 mmHg) or a decrease in the Doppler Velocity Index (DVI) by more than 50%

Valve migration: After initial correct positioning, any observed movement (upward or downward) of the TAV within the aortic annulus from its initial position, with or without consequences.

Valve embolization: The TAV moves during or after deployment such that it loses contact within the aortic annulus.

Ectopic valve deployment: Permanent deployment of the TAV in a location other than the aortic root.

TAV in TAV deployment: Additional valve prosthesis is implanted within a previously implanted TAV because of sub-optimal device position and/or function, during or after the index procedure.

Hemolysis: Red cell destruction confirmed by lab data; Minor hemolysis: No intervention required; Major hemolysis: Requires intervention (e.g. iron supplements, transfusion, invasive intervention).

Prosthetic Valve Endocarditis: Any of the following;

1) Fulfillment of the following Duke criteria for definite endocarditis:

- Histologic and/or microbiologic evidence of infection at surgery or autopsy, or
- 2 major criteria, or
- 1 major criteria or 3 minor criteria, or
- 5 minor criteria

Major Criteria:

- Blood cultures positive for Infective Endocarditis (IE)
 - Typical microorganisms consistent with IE isolated from two separate blood cultures, as noted below
 - Viridans streptococci, *Streptococcus bovis*, *Staphylococcus aureus*, or HACEK group
 - Community-acquired enterococci in the presence of a primary focus
 - Microorganisms consistent with IE isolated from persistently positive blood cultures defined as:
 - At least two positive cultures or blood samples obtained >12 hours apart, or
 - All of three, or a majority of four or more separate cultures of blood, the first and last sample obtained > one hour apart
 - Single blood culture positive for *Coxiella burnetii* or an antiphase I IG antibody titer >1:800
- Evidence of endocardial involvement
 - Positive results of echocardiography for IE defined as:
 - Oscillating intracardiac mass on a valve or supporting structures in the path of regurgitant jets or on implanted material in the absence of an anatomic explanation, or
 - Abscess, or
 - New partial dehiscence of a valvular prosthesis
 - New valvular regurgitation (worsening or changing or pre-existing murmur not sufficient)

Minor Criteria:

- Predisposition: predisposing heart condition or intravenous drug use
- Fever: temperature >38°C
- Vascular phenomena: major arterial emboli, septic pulmonary infarcts, mycotic aneurysm, intracranial hemorrhage, conjunctival hemorrhages, and Janeway's lesions
- Immunological phenomena: glomerulonephritis, Osler's nodes, Roth's spots, and rheumatoid factor
- Microbiological evidence: positive blood culture but does not meet a major criterion (as noted above) or serological evidence of active infection with organism consistent with infectious endocarditis.
- Echocardiographic findings: consistent with IE but do not meet a major criterion as noted above

If only 1 major and 1-2 minor criteria are fulfilled, or if only 3-4 minor criteria are fulfilled, the event will be coded as "possible endocarditis"

- 2) Evidence of abscess, paravalvular leak, pus, or vegetation confirmed as secondary to infection by histological or bacteriological studies during a re-operation
- 3) Findings of abscess, pus, or vegetation involving the TAV or surgical bioprosthesis at autopsy

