10.7 Sample Size Determination

As this is a descriptive study, the sample size of 75 subjects was not determined by statistical sample size methods. However, a sample size of 75 subjects is adequate to accomplish the study objectives and for an assessment of the procedural safety and efficacy of the study device in the study population.

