 - Invasive diagnostic evidence with right heart catheterization showing a pulmonary capillary wedge pressure (pulmonary artery occlusion pressure) \geq 18 mmHg, central venous pressure \geq 12 mmHg, or a cardiac index < 2.2 L/min/m²
- 4) The patient receives at least one of the following treatments specifically for HF:
 - Initiation of intravenous diuretic or vasoactive agent (e.g. inotrope, vasopressor, or vasodilator)
Note that signification augmentation of oral diuretic therapy will not be sufficient to fulfill the urgent HF visit criteria
 - Mechanical or surgical intervention, including:
 - Mechanical circulatory support (e.g. intra-aortic balloon pump, ventricular assist device, extracorporeal membrane oxygenation, total artificial heart)
 - Mechanical fluid removal (e.g. ultrafiltration, hemofiltration, dialysis)

*Note that clinic visits for scheduled administration of HF therapies or procedures (e.g. intravenous diuretics, intravenous vasoactive agents, or mechanical fluid removal) **do not** qualify as non-hospitalized HF events.*

Device Success⁶³

All of the following:

- Absence of procedural mortality, **AND**
- Correct positioning of a single prosthetic heart valve into the proper anatomical location, **AND**
- Absence of patient prosthesis-mismatch and mean aortic valve gradient < 20 mmHg (or peak velocity < 3 m/sec), **AND**
- Absence of moderate or severe prosthetic valve regurgitation.

Bioprosthetic Valve Dysfunction (BVD)⁶³: Any of the following

- **Stenosis: moderate/severe**; any of the following:
 - Peak aortic velocity > 4 m/s OR mean aortic gradient > 40 mmHg, AND EOA < 0.8 cm²
 - Peak aortic velocity > 4 m/s OR mean aortic gradient > 40 mmHg, AND EOA ≥ 0.8 cm², **AND** DVI < 0.25
 - Peak aortic velocity ≤ 4 m/s and mean aortic gradient ≤ 40 mmHg, AND EOA < 0.8 cm², **AND** DVI < 0.25
- **Paravalvular regurgitation: moderate**
- **Paravalvular regurgitation: severe**
- **Transvalvular regurgitation: moderate**
- **Transvalvular regurgitation: severe**
- **Total regurgitation: moderate**
- **Total regurgitation: severe**

Notes:

1. For subjects with BSA < 1.6 m², the EOA criteria for significant (moderate or severe) stenosis is < 0.6 cm²
2. For subjects with LVOT diameter > 2.5 cm, the DVI criteria for significant (moderate or severe) stenosis is < 0.2
3. Reporting of prosthetic valve dysfunction will be based on core lab results.

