 - Peak aortic velocity ≤ 4 m/s and mean aortic gradient ≤ 40 mmHg, AND EOA < 0.8 cm², AND DVI < 0.25

Note: In the above, for subjects with BSA < 1.6 m², the EOA criteria for significant (moderate or severe) stenosis is < 0.6 cm². Additionally, for subjects with LVOT diameter > 2.5 cm, the DVI criteria for significant (moderate or severe) stenosis is < 0.2.

- Moderate or severe paravalvular regurgitation
- Moderate or severe transvalvular regurgitation
- Moderate or severe total regurgitation

Analysis of BVD will be based on data collected on the core lab CRF. The numerator for each time point will include the number of subjects meeting any of the components of BVD. The denominator will include any subject with BVD and subjects with no evidence of BVD having evaluable data for all 4 components. BVD will be summarized with frequency counts and percentages. The components of BVD will also be summarized. The analysis will be performed using the Implanted set.

Additional Outcome Measure 12 - Bioprosthetic valve failure (BVF)⁽²⁾ at 30 days, 6 months, 1 year

Bioprosthetic valve failure (BVF) is defined as meeting any of the following:

- Autopsy findings of bioprosthetic valve dysfunction, likely related to the cause of death, or valve-related death (i.e. any death caused by bioprosthetic valve dysfunction or sudden unexplained death following diagnosis of bioprosthetic valve dysfunction)
- Repeat intervention (i.e. valve-in-valve TAVI, paravalvular leak closure or SAVR following confirmed diagnosis of bioprosthetic valve dysfunction)
- Severe bioprosthetic valve dysfunction

A Kaplan-Meier analysis as described in Section 7.2 will be performed for BVF at 30 days, 6 months, and annually through 5 years. The analysis will use the Implanted set.

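### For BSA below 1.6 m², the printed BVD stenosis rule leaves high-gradient, low-DVI valves with EOA 0.6 to below 0.8 cm² unclassified; the subclinical-thrombosis definition also lacks a connector

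*Protocol*

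**What the plan says.** **BVD.** Protocol 13.8.3, repeated in SAP 7.9.3 (outcome measure 11), gives three routes to moderate or severe stenosis:

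1. "Peak aortic velocity > 4 m/s OR mean aortic gradient > 40 mmHg, AND EOA < 0.8 cm²".
2. The same velocity or gradient condition, with EOA of 0.8 cm² or more and DVI below 0.25.
3. Velocity and gradient both at or below those limits, with EOA below 0.8 cm² and DVI below 0.25.

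A note then says that for BSA below 1.6 m² "the EOA criteria for significant (moderate or severe) stenosis is" below 0.6 cm². A second note lowers the DVI cut to 0.2 when the LVOT diameter exceeds 2.5 cm. Neither note mentions the lower EOA limit in criterion 2. SAP 7.9.3 puts in the denominator everyone with BVD, plus everyone without it who has evaluable data on all four components.

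**Subclinical thrombosis.** Protocol 13.8.2 requires thrombus "without evident clinical sequelae, causing a hemodynamic impediment meeting the following criteria". The first bullet is "Increase in aortic regurgitation to moderate to severe". The second is "An increase by more than 50% of discharge mean aortic valve gradient", with the later gradient at least 20 mmHg, "or a decrease in the Doppler Velocity Index (DVI) by more than 50" percent. The only printed disjunction is inside the second bullet. The clinical limb of the same definition does state its connector: "which is associated with any of the following clinical sequelae". SAP 7.9.3 counts thrombosis from CEC adjudications by Kaplan-Meier.

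**The concern.** Criteria 1 and 2 are meant to be complementary: for a high-gradient valve, EOA is either below the cut, which suffices, or at or above it, in which case a low DVI is also needed. If the note moves one side of the cut and not the other, a band opens between 0.6 and 0.8 cm² that neither criterion covers. A subject in that band with complete data and no moderate or severe regurgitation is then reported as evaluable without BVD, which lowers the BVD proportion.

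The thrombosis definition raises a related but weaker problem. If both bullets are needed, a thrombus that only obstructs the valve, with no sequelae and no new regurgitation, is neither clinical nor subclinical. If either suffices, it is counted. The text does not settle this.

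Thrombosis, BVD and BVF are each reported at 30 days, 6 months and annually to 5 years, which is seven time points. Estimating event rates for pivotal studies is a primary objective.

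**Working it through.** No planned power, alpha or sample-size figure is in play; Protocol 10.7 says that "the sample size of 75 subjects was not determined by statistical sample size methods". The check applies the printed rules to worked cases.

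**BVD inputs.** The three criteria and two notes are as above. From Protocol 13.3.5 and SAP 7.9.2.4, EOA = LVOT diameter² × 0.785 × DVI, where DVI = LVOT VTI / aortic valve VTI.

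Take LVOT diameter 2.1 cm, so LVOT area = 2.1² × 0.785 = 3.46 cm², with mean gradient 45 mmHg and no moderate or severe regurgitation. Only DVI varies between rows.

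| DVI | EOA (cm²) | BSA 1.5, as printed | BSA 1.5, 0.6 in all three criteria | BSA 1.8 |
|---|---|---|---|---|
| 0.17 | 0.59 | BVD (criterion 1) | BVD (1) | BVD (1) |
| 0.20 | 0.69 | **none** | BVD (2) | BVD (1) |
| 0.22 | 0.76 | **none** | BVD (2) | BVD (1) |
| 0.24 | 0.83 | BVD (2) | BVD (2) | BVD (2) |
| 0.26 | 0.90 | none | none | none |

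In the third column the classification goes from BVD to none and back as DVI and EOA improve together. At the same LVOT and gradient, the worse valve (DVI 0.20) is not BVD and the better one (DVI 0.24) is.

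**Where the reversal can occur.** For one LVOT to give both EOA of at least 0.8 and DVI below 0.25, its area must exceed 0.8 / 0.25 = 3.2 cm², so its diameter must exceed √(3.2 / 0.785) = 2.02 cm. Below that size the reversal disappears, but the gap does not: at 2.0 cm (area 3.14 cm²) EOA 0.6 needs DVI 0.191 and EOA 0.8 needs 0.255, so most of the band has DVI below 0.25.

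**What the correction leaves alone.** At BSA 1.5, EOA 0.70:
- Mean gradient 30 mmHg with velocity not above 4 m/s, DVI 0.20: no BVD before or after. This follows from the note's lower cut.
- Mean gradient 45 mmHg, DVI 0.30: no BVD before or after.

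**Thrombosis.** Assume thrombus, no sequelae and no new regurgitation; discharge gradient 8 mmHg rising to 25 mmHg; DVI 0.50 falling to 0.30.
- First bullet: not met.
- Second bullet: (25 − 8) / 8 = +213% and 25 ≥ 20, so met. The DVI fall of 40% alone would not meet it.
- Both needed: not counted. Either sufficient: counted.
- BVD does not pick it up: at LVOT 2.1 cm, EOA = 3.46 × 0.30 = 1.04 cm² and, with velocity not above 4 m/s, no stenosis criterion is met at either BSA.

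**Other outputs for valves in the BVD gap.** For BSA 1.4 to 1.59 m², EOAI runs from 0.6 / 1.59 = 0.38 to just under 0.8 / 1.4 = 0.57. Both are below the severe PPM cuts of 0.65 and, for BMI of 30 or more, 0.60.

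**The case against.** **The note may be meant to replace the cut-off throughout.** On that reading the limit in criterion 2, as the complement of criterion 1, moves too and the gap closes. This is a natural reading of intent, but neither document says it. The note states only a below-0.6 criterion, and a programmer following the SAP literally would produce the third column of the table.

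**A reader might infer that all small subjects with EOA 0.6 to 0.8 cm² are missed.** The documents do not support that. Low-gradient subjects, and high-gradient subjects with DVI at or above the cut, are non-BVD under the corrected rule as well. The gap is one cell: BSA below 1.6 m², velocity above 4 m/s or mean gradient above 40 mmHg, DVI below 0.25 (0.2 if LVOT exceeds 2.5 cm), and EOA 0.6 to below 0.8 cm².

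**A reader might infer that obstructed valves are recorded as normal.** There is no such code. Mean gradient and EOA are tabulated at each echo visit, EOAI in this range is classed as severe PPM over the BSA values shown, and repeat procedures for valve dysfunction are a separate endpoint. This limits the harm but does not correct the BVD count.

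**A reader might infer that the protocol requires both thrombosis bullets.** It prints neither all nor any. Elsewhere it marks both connectors: any of the following for BVD and BVF, all of the following for device success and heart failure hospitalization. The absence of any therefore proves no more than the absence of all. The lead-in also covers thrombus that occludes flow or interferes with function, which favours either. Requiring both is the more literal reading of a two-item list of criteria, but it is not stated. The version history says this definition was aligned with the CEC charter and code list, which are not among the documents. What stands is an unstated connector.

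**Conclusion.** The BVD gap is real on the printed text of both documents and gives a classification that cannot be intended, since a smaller orifice with the same gradient and DVI can be classed better than a larger one. The thrombosis point is secondary: an ambiguity that could exclude purely obstructive asymptomatic thrombus, depending on how the CEC reads it.

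The size is probably small. A high post-implant gradient, a low DVI, a narrow EOA band and a small BSA must coincide. The documents give no distribution of BSA or EOA and no thrombosis rate, so no expected number of subjects can be calculated. One subject is 1/75 = 1.33 percentage points if all 75 are evaluable. For BVD the direction is towards under-counting; for thrombosis it is so only if both bullets are required.

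The effect falls on additional outcome measures 9 (thrombosis) and 11 (BVD), and on 12 (BVF) so far as it depends on BVD. The key safety and efficacy endpoints are not touched. The conclusion assumes that the BVD note will be programmed as printed and that no unseen document already overrides it.

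**What to change.** In Protocol 13.8.3 and SAP 7.9.3, state that for BSA below 1.6 m² the cut-off 0.6 cm² replaces 0.8 cm² in all three stenosis criteria: EOA below 0.6 in criteria 1 and 3, and EOA of 0.6 or more in criterion 2. Keep the DVI note as it is.

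In Protocol 13.8.2, state the connector between the two subclinical-thrombosis bullets. Either of suits the lead-in, which covers obstruction as well as interference with function. Reconcile it with the CEC charter and code list, and if those already specify a rule, bring the protocol into line explicitly.

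The cost is two wording changes and one line of derivation code, with no new data. If thrombosis cases have already been adjudicated, any that turned on the connector would need a second look. Making the changes before the analysis avoids recoding after results are seen.
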